1. Welcome Basket Intervention: The Welcome Basket (WB) intervention is based in part upon the original model established in New Haven, Connecticut in 1996⁸. However, this version of the WB differs from the original in its brevity (original involved several months of follow up), use of 1-1 outreach (as opposed to group meetings), and employment of compensatory interventions. In the proposed study, Peer Support Workers (PSWs) hold 1-2 initial meetings with clients (typically 30-60 minutes) in the 2-week period before they are discharged from hospital. In these meetings they will describe the program and undertake an assessment of the individual's needs and interests as they pertain to their transition to the community. From this assessment the two core components of the intervention are initiated. First, a "welcome basket" is created based upon the assessment, containing staple supplies, plants, coupons for stores nearby the client's residence, and comfort items within a modest budget (for the purposes of this study the budget will be up to \$40/basket). The PSW also forms a plan with the client about tours of their neighbourhood to familiarize them with the local resources (e.g., low cost entertainment venues; libraries; parks; inclusive spaces) and support them as needed in building confidence in accessing their local communities. These activities will take place through weekly visits (typically 2 hours/visit) in the 4 weeks immediately following discharge. WB will be provided in combination with core Cognitive Adaptation Training (CAT) compensatory interventions¹⁴. These include the setting up and placement of a calendar, lists of daily activities, signs that prompt recall of tasks, basic organization of living space, and the use of alarms and reminders (CAT supply budget of \$25). These supports are important (and often overlooked) in many clients' efforts to establish self-sufficiency after many weeks and months in hospital where staff typically initiate and structure the majority of activities.

participants who received the WB, we observed staff and client qualitative reports of successful implementation and outcome. We also observed significant quantitative changes in community functioning (ES = 0.64), domains of quality of life (ES = .38 – 1.28), psychological community integration (ES = .51) and a trend of lower rehospitalization at 6 months post-discharge as compared with average readmission rates on referring units.

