2. Welcome Basket (Brief) Intervention: The brief version of the Welcome Basket (WBbr) was developed based upon the observation in feasibility testing that for some participants much of the benefit of this approach appeared to be centred upon the visits immediately prior and subsequent to discharge. In the WBbr the same core components will be present, albeit in an abbreviated form with one 30-60 minute visit in the week prior to discharge and a single, 3-hour visit in the week subsequent to discharge in which the welcome basket would be delivered, core CAT strategies discussed and implemented, and some basic orientation to community resources undertaken. This brief version of the intervention has not to date been studied.

Treatment As Usual

Treatment as usual (TAU) involves the typical discharge procedures for clients from Unit 2, Forensic and EPU wards at CAMH. It includes referral to outpatient psychiatric services and relevant community supports with the transition facilitated by inpatient social work staff.

Controlling for Case Management

It will be a requirement that all clients enrolled in the study are engaged in some form of community-based case management along with medical follow-up. This strategy will assist in controlling for outcome variance impacted by conditions other than the intervention being studied.

Peer Support Worker Training and Clinical Context

Inpatient and outpatient clinicians and administrators are familiar with the intervention and regarded it positively from feasibility testing through to its current, ongoing delivery. There are currently 5 Peer Support Workers on staff who are extensively trained in the WB intervention. They were initially trained by [name] who developed the original WB intervention in New Haven and were trained in compensatory intervention by CAT specialists in collaboration with Drs. [name] and [name].

Participant Allocation and Blinding

For the trial, blocked randomization at a 2:2:1 ratio (TAU:WB:WBbr) will be employed to ensure balance in sample size between treatment and control groups. Stratification will not be employed as feasibility study findings did not suggest significant variance attributable to demographic or treatment history factors. Study measures will be collected by research assistants blinded to the treatment condition.

3. What are the planned inclusion/exclusion criteria?

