1. Participants will be adults, 18 years of age or older, with a chart diagnosis of a schizophrenia spectrum mental illness or bipolar disorder with psychotic features confirmed by Module B (psychotic symptoms) of the Structured Clinical Interview for DSM-5 (SCID-

5)¹⁵. All participants will be on CAMH inpatient units at the time of recruitment and will have been in inpatient care for close to or more than 2 weeks. This timeframe is guided by the rationale and experience indicating that an overly brief period of hospitalization circumscribes the relevance of the intervention.

2. Participants will be returning to places of residence in the Greater Toronto Area (catchment of CAMH).
3. Participants must have been referred to outpatient case management.
4. Proposed housing arrangements must be stable and conducive to the intervention. If homelessness or emergency shelter residence appears likely, or boarding home policy precludes any external staff from entering the premises, such individuals will be excluded.
5. Proficiency in English.

4. What are the proposed primary and secondary outcome measures and qualitative feedback?

Primary Measure: Community Functioning will be assessed with the Multnomah Community Ability Scale (MCAS)¹⁶, a 17-item scale assessing domains of functionality including health, adjustment to living, social competence, and behavioral problems (completed at all time points). This measure best reflects the primary aim of this intervention: to support a greater degree of illness self-management, independence, and level of community activity. The MCAS will be scored based upon interviews with participants primary clinician (inpatient for baseline and case managers for post and follow up measures).

Secondary Measures (All inventories have established psychometrics with this population.)

1. Hospitalization as assessed at 4 weeks and 6 months post-discharge (number of rehospitalizations and lengths of stay captured through case manager report and verified through hospital electronic database if a CAMH hospitalization).

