2. Quality of Life (QoL) will be assessed with the Satisfaction With Life scale (SWLS)¹⁷, an 18-item scale that has subscales assessing living situation, social relationships, work, self and present life. SWLS will be assessed post intervention and at follow up (would not be valid during inpatient stay due to contextual confounds with items). QoL will also be assessed using the Social Support Survey¹⁸, a 19 item scale that measures emotional/information support, tangible support, affectionate support and positive social interaction (all time points)
3. Symptomatology will be measured using the 53 item Brief Symptom Inventory¹⁹ (all time points) and the 23 item GAIN Short Screener (GAIN-SS)²⁰ (all time points).
4. Recovery Process Engagement will be measured with the brief, 10-item version of the Personal Recovery Outcome Measure²¹ (all time points).
5. Community Involvement will be assessed with the 11 item Community Integration Scale which was developed for the At Home study with a comparable population to assesses psychological and behavioural community engagement²². Community Involvement will also be assessed with the Social Functioning Scale²³. Community Involvement will be assessed post intervention and at follow up (would not be valid

during inpatient stay due to contextual confounds with items).

6. Descriptive Measures include core demographics (gender, ethnicity, sexual orientation, age, education, etc.; assessed at time 1) and service use history (history of hospitalization, physical and mental health service use, community services; assessed at baseline and updated at each contact). Amount of contact in hours/month with a person or persons (other than providers; e.g., family) regarded as an important supports by participants will be captured. This will help in determining if non-service supports are a relevant covariate in considering outcomes.

Qualitative interviews: The current peer support workers involved with the Welcome Basket study will be asked to participate in an open-ended interview that will ask how they engage in peer support work with clients as well as successes and challenges that occur at both the individual and system level. After obtaining consent, the graduate research assistant will conduct a 1-hour interview with the peer worker (see Appendix 2).

5. What is the proposed sample size and analysis strategy?

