Following provision of written informed consent, all participants will be assessed for suitability for inclusion in the study based on the inclusion and exclusion criteria. If it is deemed necessary, research staff may review participants' CAMH medical charts to obtain additional information to confirm their eligibility or to obtain clinically relevant information for research purposes and the contact information of their case manager. The study team will also have access to the participant's health records in order to document their participation in this study into their CAMH health record. The investigator or research staff may also request information from the participant's physician and/or a member of their case management team after obtaining consent for release of personal health information to determine eligibility.

Ongoing experience with the delivery of this intervention over the past 3 years has resulted in both confidence that this study will not run into substantive challenges as well as knowledge of an array of problem mitigating strategies. Recruitment has at times slowed, though this has historically been addressed readily through meeting with managers who in turn encourage teams, engagement of the Social Work practice group, and presenting at team meetings. In this period there have been no adverse events in the delivery of this intervention, it has proven feasible, and outcomes associated with its delivery have been positive.

Additionally, as part of the CLEARR (Clinical Engagement and Research Recruitment) initiative, a delegated Research Coordinator under the supervision of a CLEARR team recruiting clinician and accountable to the Research Manager will identify potential participants and notify the research team and the participant's clinician about their eligibility to participate in the study. The clinician will then ask their client if they would be willing to meet with a study team member about participating. Only with clients' agreement will they be approached.

The delegated Research Coordinator will access personal health information (PHI) in I-CARE in order to determine eligibility of CAMH clients to participate in the research study. No PHI except MRN will be collected for this purpose and this information will be kept in a secure locked location per Research Standard Operating Procedures SOP# CR501.

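### Readmissions are captured from case manager report and the hospital database only verifies CAMH stays, so unreported admissions can be missed

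*Combined protocol and SAP*

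**What the plan says.** Section 4, Secondary Measures, item 1 defines the outcome as "Hospitalization as assessed at 4 weeks and 6 months post-discharge", covering the number of rehospitalizations and their length, "captured through case manager report and verified through hospital electronic database if a CAMH hospitalization". The case manager is the source. The database confirms, and only for stays at CAMH. No text calls for a database search in participants with no reported admission.

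Three other places bear on this:

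- Section 4, Descriptive Measures (item 6) collects service use: "history of hospitalization, physical and mental health service use, community services; assessed at baseline and updated at each contact". It is listed as descriptive, its informant is not named, and nothing links it to the readmission outcome.
- Section 7 (Recruitment, Consent, Risk and Risk Mitigation) lets research staff review CAMH charts, where deemed necessary, to confirm eligibility or "to obtain clinically relevant information for research purposes".
- Section 2, Participant Allocation and Blinding: "Study measures will be collected by research assistants blinded to the treatment condition". Nothing says that case managers are blinded.

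Section 5, analysis step 3, compares hospitalization between the full Welcome Basket (WB) and treatment as usual (TAU).

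**The concern.** When the objective source is opened to verify a report, it can remove a false report but cannot add a true admission that nobody reported. The informant therefore decides which events exist.

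The protocol gives reasons to be careful about that informant. The Introduction (Goal) names disengagement from care alongside readmission as risks that peak in the first month after discharge, so the people readmitted may include those whose case manager has lost touch. Section 2 (Peer Support Worker Training and Clinical Context) describes outpatient clinicians as knowing the intervention and viewing it favourably. WB also adds "weekly visits (typically 2 hours/visit) in the 4 weeks immediately following discharge", and the peer worker interview guide presumes links with outpatient teams. Extra contact could raise detection in WB and mask a benefit. Favourable, unblinded reporters could do the opposite.

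Service use is part of the trial hypothesis (section 1), and lower rehospitalization is one of the system priorities named in the Introduction. Equal under-capture thins an already small number of events. Unequal capture biases the comparison.

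**Working it through.** **Inputs from the protocol.** 125 participants at 2:2:1, 13% attrition and 44 completers per main arm (section 5); 38% readmitted within one year (Introduction, Goal). No six-month readmission rate is given.

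**Inputs assumed.** Capture by case manager report of 70%, 80% or 90%, equal or unequal by arm. A constant hazard over the year.

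**Step 1: the plan's own figure.** 125 × 2/5 = 50 per main arm; 50 × 0.87 = 43.5, stated as 44. For the brief arm, 25 × 0.87 = 21.75, stated as 22. Both reproduce. They size the MCAS comparison; no sizing is given for readmission.

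**Step 2: expected readmitted participants.** Six-month risk = 1 − (1 − 0.38)^0.5 = 0.213, so 44 × 0.213 = 9.4 per arm. The protocol puts the greatest risk in the first month, so a constant hazard probably understates this. As an upper bracket, if all 38% fell within six months, 44 × 0.38 = 16.7.

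**Step 3: equal capture in both arms.** Lost per arm = 44 × risk × (1 − capture).

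| Capture | Lost at 21.3% | Lost at 38% |
|---|---|---|
| 90% | 0.9 | 1.7 |
| 80% | 1.9 | 3.3 |
| 70% | 2.8 | 5.0 |

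**Step 4: unequal capture, no true effect.** Spurious difference = risk × (difference in capture). Spurious risk ratio (WB/TAU) = capture in WB ÷ capture in TAU.

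| Capture, TAU / WB | Gap at 21.3% | Gap at 38% | Risk ratio |
|---|---|---|---|
| 80% / 90% | 2.1 points | 3.8 points | 1.13 |
| 70% / 90% | 4.3 points | 7.6 points | 1.29 |
| 90% / 80% | −2.1 points | −3.8 points | 0.89 |
| 90% / 70% | −4.3 points | −7.6 points | 0.78 |

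A true risk ratio of 0.75 would appear as 0.75 × 0.90/0.80 = 0.84, as 0.75 × 0.90/0.70 = 0.96, or, with the first gap reversed, as 0.75 × 0.80/0.90 = 0.67.

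**Step 5: against sampling error.** With 44 per arm at 21.3%, the standard error of the difference is √(2 × 0.213 × 0.787/44) = 8.7 points, about twice the larger gap at that rate. Two-sided 5% power for a 37% relative reduction (the top of the range that the protocol cites from a systematic review) is about 16% with full capture and 13% with 80% capture in both arms.

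**The case against.** The best reply is that the wording does not confine the database to reported cases: checking it for every participant would also be verification. Hospitalization history is updated separately, so an admission unknown to the case manager could still surface in trial data. Section 2 (Controlling for Case Management) requires every enrolled client to be in case management, and nothing says that case manager contact differs by arm. Case managers also supply the MCAS at week 4 and month 6, so complete loss of contact would show up as missing primary data. An admission is a discrete event that leaves less room for judgement than a rating. Finally, every capture rate above is assumed, and the comparison is weak even with perfect capture.

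Much of this stands, and it limits the claim. A reader might infer that admissions will be missed, or that the database is opened only after a positive report. The text does not say either; it supports only that they can be missed. A reader might also infer a bias in favour of WB. The documents show no difference in capture and no direction. Nor do they say that participants supply the service-use update.

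What the reply does not supply is a rule. No sentence requires a search when nothing was reported or gives the service-use update a role in the outcome. The eligibility criteria ask only for referral to case management, so engagement is not assured. A case manager who is in contact well enough to rate the MCAS may still not know of a stay.

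**Conclusion.** The concern holds as a weakness in how a secondary outcome is ascertained. A more objective method is available from a database that the plan already consults, so this is more than a missing detail. On the 21% six-month rate, which rests on a constant hazard, the loss is about 1–3 readmitted participants per arm if capture is 70–90%. The spurious gap is about 2 or 4 points, in either direction, if capture is 80% against 90% or 70% against 90%. These are illustrations, not estimates.

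It would be wrong to infer that the main result is at risk: the MCAS sample size does not depend on this outcome. It would also be wrong to expect the fix to rescue the readmission comparison, which has low power at 44 per arm in any case. The fix makes the count more complete and less dependent on an informant who may know the allocation.

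**What to change.** 1. **Search everyone.** At week 4 and month 6, research staff blinded to arm search the CAMH database for all randomised participants who have not withdrawn, whether or not an admission was reported. Section 7 promises that no new data will be collected on those who terminate participation. It also lists loss to follow-up as a reason for withdrawal, so state whether such participants may still be searched.
2. **Confirm permission.** Check that consent and the section 7 chart access cover a systematic outcome search. That access is worded conditionally and sits in a paragraph mainly about eligibility. Because study participation is documented in the health record, limit the search to admission and discharge records to protect the blind.
3. **Non-CAMH stays.** Count a stay reported by the case manager or recorded in the service-use update. State who supplies that update and how conflicts between sources are settled.
4. **Sensitivity analysis.** Repeat the comparison on database-confirmed CAMH admissions only.

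The cost is a few minutes of chart search per participant; no outside data linkage is needed. Non-CAMH stays remain unverified. If staff already search for every participant, a sentence saying so settles item 1.

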The primary objective of this trial is to test a difference between the full WB intervention and the control condition with an alpha level of 0.05 and a power of 80%. An additional pilot study of the WB brief intervention is proposed with an approximate 0.05 alpha level, at 50% power. While multiple testing has not been corrected for, the intention is not to power this trial to detect these differences but rather to gather the necessary preliminary data on the average effect and variance of response in the brief intervention group to determine whether further testing is indicated and sufficient data to allow for power calculations for a follow-up trial. The target sample is thus 125 participants with a 2:2:1 randomization ratio of TAU to full WB to WB brief. Accounting for an estimated 13% attrition rate (observed in the feasibility study) this sample size would result in 44 completers/group for the main intervention and control groups and 22 completers in the brief intervention group. Based on MCAS means and the pooled standard deviation observed in the feasibility study (assuming no beneficial change in MCAS in the control group), and using a superiority trial power calculation²⁴, this sample size will allow for the detection of medium effect sizes at 80% power.

The data analysis strategy is as follows: (1) We will examine treatment and control groups at baseline on demographic variables and flag any clinically significant differences that might confound outcomes. (2) We will develop a descriptive profile of session attendance. We will consider the participant as having been exposed to the intervention if they have attended at least 50% of sessions. (3) We will compare the full WB intervention group and the control group on changes in hospitalization, community involvement, community functioning, quality of life, and symptomatology from baseline to week 4 post discharge. Analysis of variance (ANCOVA) will be used for this comparison with the above variables being the dependent measures and treatment group being the independent variable controlling for MCAS scores at baseline. (4) Differences over time in these variables from baseline, to 4 week and 6 month follow up measures will be

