analyzed using mixed-effects linear modeling. For these analyses, a time effect will reflect changes across groups over time, and the group-by-time interaction will reflect changes over time between the groups. For all analyses $p < .05$ will be used as the level of significance with Cohen's d effect sizes reported. A blinded interim analysis will be conducted to determine if the sampling estimation needs to be revised. Plotting, mean and variance estimates will be calculated using the data from the WB brief treatment arm and compared with the control and full treatment.

All interviews will be recorded and transcribed by the graduate research assistant and undergraduate volunteers. Two independent researchers will code the transcripts using thematic content analysis²⁵, in order to analyze common themes that occur within the data. The PI will resolve any discrepancies that occur within the qualitative analysis. The themes will be brought back and discussed with the peer workers and WB team. Any other comments or themes that arise from this discussion will be documented using field notes²⁶.

6. Data Management and Integrity

The basic protection against risk in this study will be provided by [name] (study PI). The PI will have primary responsibility for monitoring of participants during the entire time they participate in the study. The PI will meet regularly with study personnel to review accrued data, data confidentiality, and adherence to protocol design, recruitment, and participant complaints. During meetings the Study PI will also review the enrollment data, the accrual and integrity of clinical data, and any adverse event associated with the various components of the study. If a serious adverse event occurs during the study, it will be reported to REB.

All data pertaining to a participant's involvement in this study will be coded and stored in locked offices. This information will only be accessible to the research team. In unusual cases, a participant's research records may be released in response to a court order. If the research team learns that a participant or someone with whom the participant is involved with is in serious danger or harm, an investigator will inform the appropriate agencies as per legal or regulatory requirements.

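### Three secondary scales have no baseline, so their planned change-from-baseline analyses cannot be run as written; and no outcome, MCAS included, has a named WB–TAU contrast at 6 months.

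*Combined protocol and SAP*

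**What the plan says.** All references are to the combined protocol and SAP.

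**Measurement schedule.** Section 1 places baseline in the last week of the inpatient stay, with follow-up at 4 weeks and at 6 months after discharge. The 6-month visit is meant to show whether gains are sustained. In section 4:

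- Secondary measure 2: "SWLS will be assessed post intervention and at follow up (would not be valid during inpatient stay due to contextual confounds with items").
- Secondary measure 5, covering the Community Integration Scale and the Social Functioning Scale: "Community Involvement will be assessed post intervention and at follow up", for the same reason.
- Secondary measure 1: "Hospitalization as assessed at 4 weeks and 6 months post-discharge".
- Item 6 lists hospitalization history among the descriptive measures, "assessed at baseline and updated at each contact".
- MCAS (primary), the Social Support Survey and the symptom scales are taken at all three time points.

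**Analysis.** Section 5, step (3), compares full WB with control on "changes in hospitalization, community involvement, community functioning, quality of life, and symptomatology from baseline to week 4 post discharge", by ANCOVA with "treatment group being the independent variable controlling for MCAS scores at baseline". Step (4) covers "Differences over time in these variables from baseline, to 4 week and 6 month follow up measures will be" analysed with a mixed-effects linear model. It explains the terms: "For these analyses, a time effect will reflect changes across groups over time", and the interaction stands for between-group differences in change. It gives no time coding, no pair of groups and no contrast at a stated visit.

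**The concern.** There are two separable problems.

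1. **No baseline.** Steps (3) and (4) require a baseline that section 4 deliberately does not collect for three scales, and no alternative is given. Community involvement has no scale with a baseline at all. Rehospitalization is in a similar position unless hospitalization history is meant to serve as its baseline, which the plan does not say. The analyst would have to improvise, possibly after seeing the data.

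2. **No named 6-month contrast.** The only WB–control comparison tied to a time point is at week 4. At 6 months the plan offers the interaction, which answers a different question from whether the benefit is still there. A significant three-visit interaction on MCAS is compatible with a gain that was lost. A flat two-visit interaction is compatible both with full persistence and with no benefit at either visit. The claim about lasting benefit would then rest on a contrast chosen after the fact.

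**Working it through.** **Part 1: schedule against analysis**

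| Outcome | Baseline | 4 weeks | 6 months | Change from baseline possible? |
|---|---|---|---|---|
| MCAS, Social Support Survey, symptom scales | yes | yes | yes | yes |
| Satisfaction With Life | no | yes | yes | no |
| Community Integration Scale, Social Functioning Scale | no | yes | yes | no |
| Rehospitalization | history only, listed as descriptive | yes | yes | not defined |

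The step (3) ANCOVA itself can run on week-4 scores, because its covariate is baseline MCAS. Only the change-from-baseline wording fails there. In step (4) the baseline-anchored model fails; a two-visit model could be fitted, but it is not what is written.

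**Part 2: what the interaction can show**

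Inputs from the plan:
- Completers (section 5): 125 × 2/5 × 0.87 = 43.5, stated as 44 per main arm. This reproduces. Alpha is 0.05, taken as two-sided.
- Grid of d = 0.38, 0.51, 0.64 and 1.28, from the feasibility results in section 2. Those are changes among WB recipients, so they serve only as a range and not as between-group estimates.

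Assumed, because the documents do not give them: unit SD at each visit, and visit correlation r = 0.3, 0.5 or 0.7.

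*Three visits, categorical time, equal correlation.* Let x be the two WB–TAU differences in change from baseline: (d, d) if sustained, (d, 0) if vanished by 6 months. Each change has variance 2(1−r) and their covariance is (1−r). The noncentrality is (44/2) · x′V⁻¹x. Both patterns give x′V⁻¹x = 2d²/[3(1−r)], so the joint test has exactly the same power for either. Example: d = 0.64, r = 0.5 gives 22 × 2 × 0.4096/1.5 = 12.0, and power 0.878 (noncentral F, 2 and 172 df).

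*6-month contrast adjusted for baseline.* Noncentrality d/√[(1−r²)·2/44], 85 df.

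| d | Joint interaction, sustained or vanished (r = 0.3/0.5/0.7) | 6-month contrast, sustained | 6-month contrast, vanished |
|---|---|---|---|
| 0.38 | 0.319/0.430/0.651 | 0.455/0.530/0.694 | 0.05 |
| 0.51 | 0.533/0.688/0.896 | 0.698/0.780/0.912 | 0.05 |
| 0.64 | 0.742/0.878/0.984 | 0.875/0.929/0.986 | 0.05 |
| 1.28 | ≥0.999 | ≥0.999 | 0.05 |

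*Unequal correlation.* For MCAS the informant changes from inpatient clinician to case manager after discharge (section 4), so a weaker correlation with baseline is plausible. Take 0.3 with baseline and 0.7 between week 4 and 6 months. Then x′V⁻¹x is 0.8d² if sustained and 1.867d² if vanished. The interaction rejects 0.453 v 0.828 (sustained v vanished) at d = 0.51, and 0.653 v 0.959 at d = 0.64 (2 and 85 df).

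*Linear time in weeks (0, 4, 26).* The group-by-slope test has these powers at r = 0.3/0.5/0.7:
- d = 0.51: sustained 0.300/0.397/0.592; vanished 0.138/0.175/0.260, with opposite sign.
- d = 0.64: sustained 0.437/0.568/0.786; vanished 0.191/0.249/0.379, with opposite sign.

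*Two visits only (the three scales).* The interaction is the 4-week-to-6-month change in the group difference.
- Sustained benefit: it is d − d = 0, so the test rejects 5% of the time at any d.
- Full fade: noncentrality d√22/√[2(1−r)], which gives 0.708/0.843/0.969 at d = 0.64.
- 6-month contrast: noncentrality d√22, 86 df. Power is 0.422, 0.657, 0.843 and ≥0.999 across the four d values.

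*Precision of the 6-month contrast.* The 95% CI half-width is 0.42 SD unadjusted, and 0.40/0.37/0.30 SD adjusted for the outcome's own baseline at r = 0.3/0.5/0.7.

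**The case against.** The strongest reply is that this is a matter of wording on secondary scales. The step (3) ANCOVA runs on week-4 scores, and a two-visit mixed model can be fitted. Quality of life is only partly affected, because the Social Support Survey has a baseline. All of that is right, and it limits Part 1 to three scales and to rehospitalization. It does not supply the missing rule.

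On Part 2, the plan nowhere claims that the interaction alone proves sustainment. A categorical-visit model already contains the 6-month contrast. Step (3) also shows whether there was a week-4 difference, which helps to tell persistence from no benefit. These points stand as far as they go, but a week-4 difference followed by a non-significant interaction still does not show that the benefit is present at 6 months.

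The exact equality of power for kept and lost effects needs categorical time and equal correlations, neither of which the plan states. Under linear time the sign of the interaction does separate the two patterns, though with less power than the direct contrast. The 0.3/0.7 correlation pattern is one choice: with 0.6 between adjacent visits and 0.4 from baseline to 6 months, the vanished-v-sustained gap at d = 0.51 shrinks to 0.85 v 0.68, in the same direction. The figures are illustrations, and the argument does not depend on any one of them.

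A further fair point is that naming more tests raises multiplicity. Here the contrast takes the interaction's place as the test of sustainment, so each outcome still has one such test.

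**Conclusion.** The concern holds on both parts. The contradiction between sections 4 and 5 is plain for Satisfaction With Life, the Community Integration Scale and the Social Functioning Scale, and needs no assumption. Rehospitalization has an undefined baseline. That the interaction does not test sustainment follows from its definition for two visits. For three visits it follows under categorical time with equal variances and correlations, where at d = 0.64 the interaction rejects 0.74–0.98 for kept and lost benefits alike, against 0.87–0.99 and 0.05 for the 6-month contrast. The sizes rest on 44 per arm, a two-sided 0.05 level, assumed correlations and feasibility effect sizes used only as a grid.

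This should be fixed, but it does not undermine the trial. The sample size and the week-4 MCAS comparison are untouched. The plan does not itself label week 4 as the primary time point; that is inferred here from step (3).

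**What to change.** Amend section 5 before unblinding:

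- **Satisfaction With Life, Community Integration Scale, Social Functioning Scale.** Remove change from baseline. Fit a repeated-measures model with visit (4 weeks, 6 months), group and group-by-visit, adjusted for baseline MCAS. Report the WB–TAU contrast with 95% CI at each visit.
- **Outcomes measured at all three time points, including MCAS.** Keep the baseline-to-6-month model and state that visit is categorical. Name the WB–TAU contrast at 6 months, adjusted for that outcome's own baseline and with 95% CI, as the test of sustainment. Own-baseline adjustment is what gives the narrower intervals shown above. Use the interaction only to describe the course over time.
- **Rehospitalization.** Compare number and length of stay between groups at 4 weeks and 6 months, not as change from baseline, with the model named in advance (negative binomial regression is one option). If hospitalization history is meant as a baseline, say so.

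The cost is analysis-plan wording only. No new data, visits or participants are needed, and the sample size and the week-4 MCAS analysis stay as they are.
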